2.5.5 Unscheduled visits

Unscheduled visit measurements of laboratory data, vital signs, and ECG will be included in the by-visit summaries, computation of baseline, worst values, and PCSAs.

2.5.6 Pooling of centers for statistical analyses

Due to small sample size in some countries, the countries will be pooled into regions as defined below for the analyses:

- East Europe: Poland, Russia, Turkey and Ukraine
- Latin America: Argentina, Chile and Mexico
- North America: USA

2.5.7 Statistical technical issues

Not applicable.

3 INTERIM ANALYSIS

No formal interim analysis is planned. Analyses will be performed for safety/efficacy monitoring and internal decision making. The analyses will be conducted by individuals independent of the study and the development program and reviewed by an independent Data Monitoring Committee (DMC). No formal stopping rules or adjustment for multiplicity will be applied. Full details on DMC procedures and data to be reviewed are described in the DMC charter.

4 DATABASE LOCK

A core database lock is planned to occur approximately 4 weeks after all patients have completed End of Treatment visit. The final database is planned to be locked 4 weeks after last patient last visit.

5 SOFTWARE DOCUMENTATION

All summaries and statistical analyses will be generated using SAS version 9.4 or higher.

Appendix A Potentially clinically significant abnormalities criteria

CRITERIA for POTENTIALLY CLINICALLY SIGNIFICANT ABNORMALITIES for phase 2/3 studies (oncology excepted)

(From BTD-009536 "Analysis and reporting of safety data from clinical trials through the Clinical Study Report"
Version 3, 21-MAY-2014)

Parameter	PCSA	Comments
Clinical Chemistry		
ALT	By distribution analysis : >3 ULN >5 ULN >10 ULN >20 ULN	Enzymes activities must be expressed in ULN, not in IU/L. Concept paper on DILI – FDA draft Guidance Oct 2007. Internal DILI WG Oct 2008. Categories are cumulative. First row is mandatory. Rows following one mentioning zero can be deleted.
AST	By distribution analysis : >3 ULN >5 ULN >10 ULN >20 ULN	Enzymes activities must be expressed in ULN, not in IU/L. Concept paper on DILI – FDA draft Guidance Oct 2007. Internal DILI WG Oct 2008. Categories are cumulative. First row is mandatory. Rows following one mentioning zero can be deleted.
Alkaline Phosphatase	>1.5 ULN	Enzymes activities must be expressed in ULN, not in IU/L. Concept paper on DILI – FDA draft Guidance Oct 2007. Internal DILI WG Oct 2008.
Total Bilirubin	>1.5 ULN >2 ULN	Must be expressed in ULN, not in $\mu\text{mol}/\text{L}$ or mg/L . Categories are cumulative. Concept paper on DILI – FDA draft Guidance Oct 2007. Internal DILI WG Oct 2008.
Conjugated Bilirubin >35% Total Bilirubin and TBILI>1.5 ULN		Conjugated bilirubin dosed on a case-by-case basis.
ALT and Total Bilirubin	ALT>3 ULN and TBILI>2 ULN	Concept paper on DILI – FDA draft Guidance Oct 2007. Internal DILI WG Oct 2008. To be counted within a same treatment phase, whatever the interval between measurement.

**CRITERIA for POTENTIALLY CLINICALLY SIGNIFICANT ABNORMALITIES
for phase 2/3 studies (oncology excepted)**

*(From BTD-009536 "Analysis and reporting of safety data from clinical trials through the Clinical Study Report"
Version 3, 21-MAY-2014)*

Parameter	PCSA	Comments
CPK	>3 ULN >10 ULN	FDA Feb 2005. Am J Cardiol April 2006. Categories are cumulative. First row is mandatory. Rows following one mentioning zero can be deleted.
CLcr (mL/min) (Estimated creatinine clearance based on the Cokcroft-Gault equation)	<15 (end stage renal disease) ≥15 - <30 (severe decrease in GFR) ≥30 - < 60 (moderate decrease in GFR) ≥60 - <90 (mild decrease in GFR) ≥ 90 (normal GFR)	FDA draft Guidance 2010 Pharmacokinetics in patients with impaired renal function-study design, data analysis, and impact on dosing and labeling
eGFR (mL/min/1.73m ²) (Estimate of GFR based on an MDRD equation)	<15 (end stage renal disease) ≥15 - <30 (severe decrease in GFR) ≥30 - < 60 (moderate decrease in GFR) ≥60 - <90 (mild decrease in GFR) ≥ 90 (normal GFR)	FDA draft Guidance 2010 Pharmacokinetics in patients with impaired renal function-study design, data analysis, and impact on dosing and labeling
Creatinine	≥150 µmol/L (Adults) ≥30% change from baseline ≥100% change from baseline	Benichou C., 1994.
Uric Acid		Harrison- Principles of internal Medicine 17 th Ed., 2008.
Hyperuricemia	>408 µmol/L	
Hypouricemia	<120 µmol/L	
Blood Urea Nitrogen	≥17 mmol/L	
Chloride	<80 mmol/L ≥115 mmol/L	
Sodium	≤129 mmol/L ≥160 mmol/L	
Potassium	<3 mmol/L ≥5.5 mmol/L	FDA Feb 2005.
Total Cholesterol	≥7.74 mmol/L	Threshold for therapeutic intervention.
Triglycerides	≥4.6 mmol/L	Threshold for therapeutic intervention.
Lipasemia	≥3 ULN	
Amylasemia	≥3 ULN	

**CRITERIA for POTENTIALLY CLINICALLY SIGNIFICANT ABNORMALITIES
for phase 2/3 studies (oncology excepted)**

*(From BTD-009536 "Analysis and reporting of safety data from clinical trials through the Clinical Study Report"
Version 3, 21-MAY-2014)*

Parameter	PCSA	Comments
Glucose		
Hypoglycaemia	≤ 3.9 mmol/L and $< LLN$	ADA May 2005.
Hyperglycaemia	≥ 11.1 mmol/L (unfasted); ≥ 7 mmol/L (fasted)	ADA Jan 2008.
HbA1c	$> 8\%$	
Albumin	≤ 25 g/L	
CRP	> 2 ULN or > 10 mg/L (if ULN not provided)	FDA Sept 2005.
Hematology		
WBC	< 3.0 Giga/L (Non-Black); < 2.0 Giga/L (Black) ≥ 16.0 Giga/L	Increase in WBC: not relevant. To be interpreted only if no differential count available.
Lymphocytes	> 4.0 Giga/L	
Neutrophils	< 1.5 Giga/L (Non-Black); < 1.0 Giga/L (Black)	International Consensus meeting on drug-induced blood cytopenias, 1991. FDA criteria.
Monocytes	> 0.7 Giga/L	
Basophils	> 0.1 Giga/L	
Eosinophils	> 0.5 Giga/L or $> ULN$ (if $ULN \geq 0.5$ Giga/L)	Harrison- Principles of internal Medicine 17 th Ed., 2008.
Hemoglobin	≤ 115 g/L (Male); ≤ 95 g/L (Female) ≥ 185 g/L (Male); ≥ 165 g/L (Female) Decrease from Baseline ≥ 20 g/L	Criteria based upon decrease from baseline are more relevant than based on absolute value. Other categories for decrease from baseline can be used (≥ 30 g/L, ≥ 40 g/L, ≥ 50 g/L).
Hematocrit	≤ 0.37 v/v (Male) ; ≤ 0.32 v/v (Female) ≥ 0.55 v/v (Male) ; ≥ 0.5 v/v (Female)	
RBC	≥ 6 Tera/L	Unless specifically required for particular drug development, the analysis is redundant with that of Hb. Otherwise, consider FDA criteria.
Platelets	< 100 Giga/L ≥ 700 Giga/L	International Consensus meeting on drug-induced blood cytopenias, 1991.

**CRITERIA for POTENTIALLY CLINICALLY SIGNIFICANT ABNORMALITIES
for phase 2/3 studies (oncology excepted)**

*(From BTD-009536 "Analysis and reporting of safety data from clinical trials through the Clinical Study Report"
Version 3, 21-MAY-2014)*

Parameter	PCSA	Comments
Urinalysis		
pH	≤4.6 ≥8	
Vital signs		
HR	≤50 bpm and decrease from baseline ≥20 bpm ≥120 bpm and increase from baseline ≥20 bpm	To be applied for all positions (including missing) except STANDING.
SBP	≤95 mmHg and decrease from baseline ≥20mmHg ≥160 mmHg and increase from baseline ≥20 mmHg	To be applied for all positions (including missing) except STANDING.
DBP	≤45 mmHg and decrease from baseline ≥10 mmHg ≥110 mmHg and increase from baseline ≥10 mmHg	To be applied for all positions (including missing) except STANDING.
Orthostatic Hypotension		
Orthostatic SDB	≤-20 mmHg	
Orthostatic DBP	≤-10 mmHg	
Weight	≥5% increase from baseline ≥5% decrease from baseline	FDA Feb 2007.

**CRITERIA for POTENTIALLY CLINICALLY SIGNIFICANT ABNORMALITIES
for phase 2/3 studies (oncology excepted)**

*(From BTD-009536 "Analysis and reporting of safety data from clinical trials through the Clinical Study Report"
Version 3, 21-MAY-2014)*

Parameter	PCSA	Comments
ECG		Ref.: ICH E14 guidance (2005) and E14 Q&A (2012), and Cardiac Safety Research Consortium White Paper on PR and QRS (Nada et al. Am Heart J. 2013; 165(4) : 489-500)
HR	<50 bpm <50 bpm and decrease from baseline ≥20 bpm <40 bpm <40 bpm and decrease from baseline ≥20 bpm <30 bpm <30 bpm and decrease from baseline ≥20 bpm >90 bpm >90 bpm and increase from baseline ≥20bpm >100 bpm >100 bpm and increase from baseline ≥20bpm >120 bpm >120 bpm and increase from baseline ≥20 bpm	Categories are cumulative
PR	>200 ms >200 ms and increase from baseline ≥25% > 220 ms >220 ms and increase from baseline ≥25% > 240 ms > 240 ms and increase from baseline ≥25%	Categories are cumulative
QRS	>110 ms >110 msec and increase from baseline ≥25% >120 ms >120 ms and increase from baseline ≥25%	Categories are cumulative
QT	>500 ms	

**CRITERIA for POTENTIALLY CLINICALLY SIGNIFICANT ABNORMALITIES
for phase 2/3 studies (oncology excepted)**

*(From BTD-009536 "Analysis and reporting of safety data from clinical trials through the Clinical Study Report"
Version 3, 21-MAY-2014)*

Parameter	PCSA	Comments
QTc	Absolute values (ms) >450 ms >480 ms >500 ms Increase from baseline Increase from baseline]30-60] ms Increase from baseline >60 ms	To be applied to any kind of QT correction formula. Absolute values categories are cumulative QTc >480 ms and $\Delta QTc > 60$ ms are the 2 PCSA categories to be identified in individual subjects/patients listings.

Appendix B Asthma Symptom Score Numerical Rating Scale (NRS)

Morning Diary:

Please rate your asthma symptoms since last night

[figure not shown]
- No asthma symptoms, slept through the night
- Slept well, but some complaints in the morning. No nighttime awakenings
- Woke up once because of asthma (including early awakening)
- Woke up several times because of asthma (including early awakening)
- Bad night, awake most of the night because of asthma

Evening Diary:

Please rate your asthma symptoms since this morning

- Very well, no asthma symptoms
- One episode of wheezing, cough, or breathlessness
- More than one episode of wheezing, cough, or breathlessness without interference with normal activities
- Wheezing, cough, or breathlessness most of the day, which interfered to some extent with normal activities
- Asthma very bad. Unable to carry out daily activities as usual

Appendix C Asthma Control Questionnaire 5-Question Version

[figure not shown]

The Asthma Control Questionnaire is copyrighted. It may not be altered, sold (paper or electronic), translated or adapted for another medium without the permission of Elizabeth Juniper.

[figure not shown]
December 2002

SYMPTOMS ONLY MODIFIED 30 JAN 04

NORTH AMERICAN ENGLISH

[figure not shown]
Appendix D Asthma Quality of Life Questionnaire

[figure not shown]

[figure not shown]
© The Asthma Quality of Life Questionnaire with Standardised Activities (AQLQ(S)) is copyrighted and all rights are reserved. No part of this questionnaire may be sold, modified or reproduced in any form without the express permission of Elizabeth Juniper on behalf of QOL Technologies Limited

[figure not shown]
APRIL 2008

[figure not shown]
Modified September 2010
AQLQ(S)-SA North American English Version

[figure not shown]

[figure not shown]

[figure not shown]
Appendix E Standardized Rhinoconjunctivitis Quality of Life Questionnaire RQLQ(S)

[figure not shown]

[figure not shown]
© The RQLQ(S) is copyrighted. It may not be altered, sold (paper or electronic), translated or adapted for another medium without the permission of Elizabeth Juniper.

NOVEMBER 2001

Appendix F List of opportunistic infections

- Aspergillosis
- Blastomyces dermatitidis (endemic in the south-eastern and south-central states US, along Mississippi and Ohio Rivers)
- Candidiasis – only systemic or extensive mucosal or cutaneous candidiasis.
- Coccidioides immitis (endemic south-western US and Central and South America)
- Cryptococcus
- Cytomegalovirus
- Herpes Simplex (severe/disseminated)
- Herpes Zoster
- Histoplasmosis (pulmonary or disseminated; most common tropical areas Tennessee-Ohio-Mississippi river basins)
- Listeriosis
- Mycobacterium avium
- Nontuberculosis mycobacteria
- Pneumocystis pneumonia (PCP)
- Tuberculosis (TB)

This list is indicative and not exhaustive.

Appendix G Definition of Anaphylaxis

“Anaphylaxis is a serious allergic reaction that is rapid in onset and may cause death.”

(Adapted from Sampson HA, Munoz-Furlong A, Campbell RL, Adkinson NF, Bock SA, Branum A, et al. *Second symposium on the definition and management of anaphylaxis: Summary report—Second National Institute of Allergy and Infectious Disease/Food Allergy and Anaphylaxis Network symposium. J Allergy Clin Immunol 2006;117:391-7*)

Clinical criteria for diagnosing anaphylaxis

Anaphylaxis is highly likely when any one of the following 3 criteria are fulfilled:

1. Acute onset of an illness (minutes to several hours) with involvement of the skin, mucosal tissue, or both (eg, generalized hives, pruritus or flushing, swollen lips-tongue-uvula)
AND AT LEAST ONE OF THE FOLLOWING
 - a. Respiratory compromise (eg, dyspnea, wheeze-bronchospasm, stridor, reduced PEF, hypoxemia)
 - b. Reduced BP or associated symptoms of end-organ dysfunction (eg, hypotonia [collapse], syncope, incontinence)
2. Two or more of the following that occur rapidly after exposure to *a likely allergen for that patient* (minutes to several hours):
 - a. Involvement of the skin-mucosal tissue (eg, generalized hives, itch-flush, swollen lips-tongue-uvula)
 - b. Respiratory compromise (eg, dyspnea, wheeze-bronchospasm, stridor, reduced PEF, hypoxemia)
 - c. Reduced BP or associated symptoms (eg, hypotonia [collapse], syncope, incontinence)
 - d. Persistent gastrointestinal symptoms (eg, crampy abdominal pain, vomiting)
3. Reduced BP after exposure to *known allergen for that patient* (minutes to several hours):
 - a. Infants and children: low systolic BP (age specific) or greater than 30% decrease in systolic BP*
 - b. Adults: systolic BP of less than 90 mm Hg or greater than 30% decrease from that person's baseline

PEF, Peak expiratory flow; *BP*, blood pressure.

*Low systolic blood pressure for children is defined as less than 70 mm Hg from 1 month to 1 year, less than (70 mm Hg + [2 × age]) from 1 to 10 years, and less than 90 mm Hg from 11 to 17 years.

Appendix H Technical details of sensitivity analysis

Change from baseline in FEV1

Multiple imputation

1. Partially impute data using Markov Chain Monte Carlo method to obtain 40 datasets with monotone missing pattern:

```
proc mi data=&DSTIN seed=&seed nimpute=40 out=monotone;
  mcmc impute=monotone;
  var base &chg_all;
run;
```

where &chg_all includes change from baseline in FEV1 at all visits.

2. For each of the imputed dataset with monotone missing pattern, the remaining missing data will be imputed by a regression model

```
proc mi data=monotone seed=&seed nimpute=1 out=data_imp;
  by _imputation_;
  class trt01pn sex eosbgp1n cntygr1 icsgrp;
  var sex htbl eosbgp1n cntygr1 trt01pn icsgrp base
  &chg_all;
  monotone reg;
run;
```

3. Analyze the 40 imputed datasets by the ANCOVA model described in [Section 2.4.4.2](#):

```
proc glm data=data_imp;
  by _imputation_;
  class trt01pn sex eosbgp1n cntygr1 icsgrp;
  model chg_12 = trt01pn sex htbl eosbgp1n cntygr1 icsgrp
  base;
  lsmeans trt01pn / stderr;
  estimate "SAR440340 vs Placebo" trt01pn -1 1 0 0;
  estimate "Coadministration vs Placebo" trt01pn -1 0 1 0;
  estimate "Coadministration vs SAR440340" trt01pn 0 -1 1 0;
  estimate "Coadministration vs Dupilumab" trt01pn 0 0 1 -1;
  estimate "Dupilumab vs Placebo" trt01pn -1 0 0 1;
  ods output LSMeans = LSMeans_imp Estimates = Diff_imp;
run;
```

4. Apply Rubin's rule to combine analysis results:

```
proc sort data=LSMeans_imp;
  by trt01pn _imputation_;
```

```
run;

proc mianalyze data=LSMeans_imp;
  by trt01pn;
  modeleffects lsmean;
  stderr stderr;
  ods output ParameterEstimates=LSMeans;
run;

proc mianalyze data= Diff_imp;
  modeleffects estimate;
  stderr stderr;
  ods output ParameterEstimates=LSDiff;
run;
```

Control-based multiple imputation

This approach is similar to the standard method described above, except for Step 2. After obtaining datasets with monotone missing patterns in Step 1, the following steps will be repeated to sequentially impute missing data at each time point:

- 1) For time point t , separate the imputed datasets into two parts: `imp_&t`, containing all placebo patients and those from the active treatment groups that have missing change from baseline in FEV1 at time t ; and `rest_&t`, containing the rest of the patients from the active treatment groups.
- 2) Impute missing values at t based on the model estimated from placebo group patients:

```
proc mi data=imp_&t seed=&seed.&t n impute=1
out=imputed_&t;
  by _imputation_;
  class sex eosbgp1n cntygr1 icsgrp;
  var sex htbl eosbgp1n cntygr1 icsgrp base
    &chg_prior chg_&t;
  monotone reg (chg_&t);
run;
```

where `chg_&t` is change from baseline in FEV1 at t and `&chg_prior` includes change from baseline in FEV1 at all visits prior to t . No prior value will be included when imputing the first post-randomization time point.

- 3) Combine the imputed data `imputed_&t` with `rest_&t`.

ACT15102-16-1-9-sap

ELECTRONIC SIGNATURES

Signed by	Meaning of Signature	Server Date (dd-MMM-yyyy HH:mm)
[REDACTED]	Clinical Approval	[REDACTED]
[REDACTED]	Clinical Approval	[REDACTED]

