2.4.4 Analyses of efficacy endpoints

All efficacy endpoints will be analyzed using the mITT population. [Table 4](#) summarizes the pairwise comparisons to be conducted in accordance with study objectives. Each comparison on each endpoint will be tested at a two-sided 5% significance level.

Table 4 - Pairwise comparisons and study objectives

	Primary endpoint	Secondary endpoints	Other efficacy endpoints
SAR440340 vs. placebo	P	S	O
Coadministration of SAR440340 and dupilumab vs. placebo	P	S	O
Coadministration of SAR440340 and dupilumab vs. SAR440340	O	S	O
Coadministration of SAR440340 and dupilumab vs. dupilumab	O	S	O
Dupilumab vs. placebo (as calibrator only)	O	O	O

P: Primary objective; S: Secondary objective; O: Other objective

2.4.4.1 Analysis of primary efficacy endpoint(s)**Main statistical model and adjustment of covariates**

The primary endpoint of incidence of LOAC will be analyzed using a logistic regression model. The model will include terms for treatment, baseline eosinophil strata, region (pooled countries), background ICS dose level at randomization and number of exacerbation events within 1 year prior to screening.

For each pairwise treatment comparison, the odds ratio, and corresponding 95% confidence interval (CI) and two-sided p-value will be derived from this model. Sample SAS code is provided below:

```
proc genmod data=loacdata descending;
  class trt01pn eosbgp1n cntygr1 icsgrp;
  model resp = trt01pn eosbgp1n cntygr1 icsgrp asmanum /dist=bin
link=logit type3;
  estimate "SAR440340 vs Placebo"      trt01pn -1 1 0 0 / exp;
  estimate "Coadministration vs Placebo" trt01pn -1 0 1 0 / exp;
  estimate "Coadministration vs SAR440340" trt01pn 0 -1 1 0 / exp;
  estimate "Coadministration vs Dupilumab" trt01pn 0 0 1 -1 / exp;
  estimate "Dupilumab vs Placebo"        trt01pn -1 0 0 1 / exp;
  ods output Estimates = Estimates;
run;
```

All reported LOAC events will undergo the standard medical review process to ensure the events are in-line with the protocol definition. For patients discontinued due to a reason other than LOAC, but for which LOAC could be suspected, the case will be medically reviewed, with appropriate queries sent to the respective site, for final determination of LOAC status to be recorded in the clinical database prior to database lock. As such, there should not be missing data for the primary LOAC endpoint.

Supportive analysis

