The repeated measures analysis will be based on the restricted maximum likelihood method assuming an unstructured covariance to model the within-subject errors. A Kenward-Roger approximation will be used for the denominator degree of freedom. Descriptive statistics including number of patients, mean, standard error, and least squares (LS) means will be provided for each treatment group. Difference in LS means and the corresponding two-sided 95% CI and p-value will be provided for each pairwise treatment comparison. Sample SAS code can be found below:

```

proc mixed data=fev1data method=reml;
  class usubjid trt01pn sex cntygr1 eosbgp1n icsgrp avisitn;
  model chg = trt01pn sex hgtbl cntygr1 eosbgp1n icsgrp avisitn
    trt01pn*avisitn base base*avisitn /ddfm=kr residual;
  repeated avisitn / subject=usubjid type=un;
  lsmeans trt01pn*avisitn / pdiff cl;
  ods output LSMeans=LSMeans Diffs=Diffs;
run;

```

If the above model fails to converge, the specification may be changed as follows: 1) use maximum likelihood estimation instead of restricted maximum likelihood method; 2) specify a different covariance structure to reduce the number of unknown parameters to be estimated, the path will be UN→TOEPH→TOEP→AR(1).

Sensitivity analysis

The following sensitivity analyses will be conducted to assess the robustness of the main model:

Analyses using the same MMRM model and estimation methods as specified above:

- *Sensitivity analysis 1:* Inclusion of all FEV1 measurements collected up to EOT for all patients. Missing data will not be imputed.
- *Sensitivity analysis 2: Per protocol analysis*

Exclusion of post-baseline FEV1 measurements in patients (and within time windows) where the patient had a protocol deviation considered to have a potential impact on efficacy, ie, (1) intake of a prohibited medication(s); (2) IMP and/or required background therapy non-compliance; (3) entry criteria violation. Deviations will be medically/clinically reviewed during the study, with final classification made and recorded prior to database lock. Missing data will not be imputed.

Analyses with imputation for missing FEV1:

- *Sensitivity analysis 3: Multiple imputation*

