Missing pre-BD/post-BD FEV1 values will be imputed multiple times using a regression model. Imputation will be conducted sequentially as the imputation for each visit will incorporate information from prior visits. Specifically, the covariates to be included are treatment group, gender, baseline height, baseline eosinophil strata, region, background ICS dose level at randomization, baseline value, and change from baseline in FEV1 at all prior visits. Forty imputations will be performed. For each imputation, the change from baseline in pre-BD/post-BD FEV1 at Week 12 will be analyzed by an ANCOVA model with treatment, gender, height, baseline value, baseline eosinophil strata, region, and background ICS dose level at randomization as covariates. Valid statistical inference will be generated by combining results from these 40 analyses using Rubin's rule.

- *Sensitivity analysis 4: Control-based multiple imputation*

This approach assumes that after treatment discontinuation, patients from the active treatment groups will exhibit the same future evolution as those in the placebo group. The implementation is similar to that of the standard multiple imputation approach above (sensitivity analysis 3), except when fitting the imputation model, only data from the placebo group will be used and treatment will not be included as a covariate.

Technical details are provided in [Appendix H](#).

Subgroup analysis

Subgroup analyses of change from baseline in pre-BD and post-BD FEV1 will be conducted in the same subgroups as defined for the primary endpoint based on the primary analysis method for the secondary endpoints. Within each subgroup, descriptive statistics including number of patients, mean, standard error, and LS means will be provided for each treatment group. Difference in LS means and the corresponding two-sided 95% CI will be provided for each pairwise treatment comparison.

Treatment-by-subgroup interaction at Week 12 and its p-value will be derived from a MMRM model. The model will include change from baseline in FEV1 values up to week 12 following the rules in [Table 5](#). Treatment, gender, baseline height, baseline eosinophil strata, region, background ICS dose level at randomization, visit, treatment by-visit interaction, baseline value, baseline-by-visit interaction, subgroup (if different from the aforementioned covariates), subgroup-by-treatment interaction and subgroup-by-treatment-by-visit interaction will be the covariates.

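### SAP Appendix H pools the five FEV1 treatment differences as if they were one parameter, so sensitivity analyses 3 and 4 as coded yield a single meaningless row instead of five comparisons

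*SAP*

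**What the plan says.** SAP 2.4.4.2 defines sensitivity analysis 3 as standard multiple imputation and sensitivity analysis 4 as control-based imputation. Under the former it asks for 40 imputed datasets, an ANCOVA on each, and pooling: "Valid statistical inference will be generated by combining results from these 40 analyses using Rubin's rule". It refers to Appendix H for the technical details.

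Table 4 in SAP 2.4.4 lists five pairwise comparisons, and the text there states: "Each comparison on each endpoint will be tested at a two-sided 5% significance level". For FEV1, four of the five serve secondary objectives; dupilumab versus placebo is the calibrator. For the main FEV1 model, 2.4.4.2 spells out the output: "Difference in LS means and the corresponding two-sided 95% CI and p-value will be provided for each pairwise treatment comparison".

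In Appendix H, Step 3 fits the ANCOVA by imputation with five ESTIMATE statements and writes the results with "ods output LSMeans = LSMeans_imp Estimates = Diff_imp". Step 4 then has two pooling blocks:

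- LS means: a PROC SORT by treatment and imputation, then "proc mianalyze data=LSMeans_imp" with a BY statement on treatment.
- Differences: "proc mianalyze data= Diff_imp", then only the MODELEFFECTS and STDERR statements and "ods output ParameterEstimates=LSDiff". There is no sort and no BY.

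Of the control-based method the appendix says: "This approach is similar to the standard method described above, except for Step 2". It therefore uses the same Step 4.

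**The concern.** Rubin's rule combines repeated estimates of one quantity. The difference block gives the procedure five quantities mixed together with nothing to tell them apart. It can return only one pooled row, and that row is none of the planned comparisons.

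Analyses 3 and 4 are the only two FEV1 sensitivity analyses that impute missing values. Table 5 of the SAP deliberately sets FEV1 to missing after LOAC with rescue medication or after OCS use, so these two analyses are the plan's check on how that missingness is handled. As coded, they supply no valid SE, CI or p-value for any difference in pre- or post-bronchodilator FEV1. A point difference could still be obtained by subtracting two pooled arm means, but without its precision.

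**Working it through.** **1. Number of rows pooled.** The SAP's stated figure is 40 analyses per pooled result.

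- LS means block: 4 arms × 40 = 160 rows, split by treatment into 4 groups of 40. This agrees with the SAP.
- Difference block: 5 contrasts × 40 = 200 rows, not split, so one group of 200. This does not.

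**2. What the single row estimates.** The coefficients in Step 3, in the order placebo (P), SAR440340 (S), coadministration (C), dupilumab (D), are:

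| Contrast | P | S | C | D |
|---|---|---|---|---|
| S − P | −1 | 1 | 0 | 0 |
| C − P | −1 | 0 | 1 | 0 |
| C − S | 0 | −1 | 1 | 0 |
| C − D | 0 | 0 | 1 | −1 |
| D − P | −1 | 0 | 0 | 1 |
| Sum | −3 | 0 | 3 | 0 |
| Mean (sum ÷ 5) | −0.6 | 0 | 0.6 | 0 |

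The pooled estimate is the mean of all rows, hence 0.6 × (C − P). This is algebra and needs no assumption about the data.

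**3. What happens to the standard error.** Rubin's total variance is T = U + (1 + 1/m)B, with U the mean within-imputation variance and B the variance of the pooled estimates. With five contrasts mixed,

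B = [40 × Σ(d_j − d̄)² + 5 × 39 × b²] / 199,

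where d_j are the five true differences, d̄ is their mean and b is the genuine between-imputation SD of a contrast. The first term has nothing to do with missing data.

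Inputs:

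- SD 0.35 L and 50 patients per arm (Protocol, Clinical Trial Summary, sample size), so √U = 0.35 × √(2/50) = 0.070 L and U = 0.0049.
- b = 0.01 to 0.04 L. This is an assumption; the documents give no value.

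Scenario A, all three active arms 0.20 L above placebo, b = 0.02:

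- d = (0.20, 0.20, 0, 0, 0.20), d̄ = 0.120, Σ(d_j − d̄)² = 3 × 0.08² + 2 × 0.12² = 0.048.
- B = (40 × 0.048 + 195 × 0.0004)/199 = (1.920 + 0.078)/199 = 0.01004.
- T = 0.0049 + 1.005 × 0.01004 = 0.01499, so SE = 0.122.
- Row: 0.120 L, 95% CI −0.121 to 0.361, p 0.33 (439 df).
- Correct pooling of S − P with m = 40: T = 0.0049 + 1.025 × 0.0004 = 0.00531, SE 0.073. Result 0.200 L, p 0.006.

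Over the range of b:

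| Scenario | Row as coded | Row SE | Row p | Correctly pooled |
|---|---|---|---|---|
| A: S = C = D = +0.20 L | 0.120 L | 0.121–0.127 | 0.32–0.35 | S − P 0.200 L, SE 0.071–0.081, p 0.005–0.014 |
| B: C = D = +0.27 L; S = 0 or 0.27 L | 0.162 L | 0.151–0.155 | 0.28–0.30 | C − P 0.270 L, p ≤ 0.001 |
| B: C = D = +0.27 L; S = 0.14 L | 0.162 L | 0.124–0.130 | 0.19–0.21 | C − P 0.270 L, p ≤ 0.001 |
| No differences between arms | 0 | 0.071–0.080 | – | SE 0.071–0.081 |

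The 0.27 L is the dupilumab effect quoted in the protocol's sample size text; 0.14 L is its smallest significant difference. In scenario B the point estimate does not move whether SAR440340 has no effect or the full effect. The SE is inflated when the contrasts differ, and is about right only when no arm differs from another.

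**4. Sensitivity to the number per arm.** After imputation nearly all randomized patients enter the ANCOVA, so 60 per arm is arguably the better figure. Then √U = 0.35 × √(2/60) = 0.064 L, and the row SEs are 0.118–0.124 in A and 0.148–0.153 in B with S = 0 or 0.27 L. The picture is the same.

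**The case against.** The best case for leaving this alone is that the method is specified correctly in the text and only the code slips. The prose asks for Rubin's rule over 40 analyses, the neighbouring block shows the right pattern, and the listing is plainly a template: it needs macro variables that are not supplied and has other typographical faults. A programmer who needs five differences and gets one unlabelled row would probably notice. The 40 estimates and SEs per contrast remain in the stored dataset, so correct pooling needs no re-analysis. The stakes are limited too: two sensitivity analyses of secondary endpoints in a Phase 2a study with nominal p-values.

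Most of this is fair, and it bounds the importance of the point. It does not remove it. Appendix H is where the SAP sends the reader for the technical specification, and what is printed there contradicts 2.4.4.2 and Table 4. If a programmer repairs it, that repair should be in the SAP before database lock, not an undocumented departure from it.

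Two uncertainties remain. That PROC MIANALYZE counts every input row as an imputation when no BY is given is standard SAS behaviour, but it is not stated in the documents and was not run here. A line lost in converting the PDF cannot be wholly excluded, but both a sort and a BY would have to be lost while both survive in the adjacent block.

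**Conclusion.** The concern holds. The printed difference-pooling step is wrong for sensitivity analyses 3 and 4, for both pre- and post-bronchodilator FEV1, and none of the five planned differences would get a valid SE, CI or p-value from it. The factor 0.6 and the zero weight on the SAR440340 and dupilumab arms are exact, given the printed contrasts and the usual behaviour of the procedure. The SEs and p-values above are illustrations that depend on the assumed effects and between-imputation SD. The pooled arm LS means, the primary LOAC analysis, the main FEV1 MMRM and sensitivity analyses 1 and 2 are not touched. It should be fixed before the database lock.

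**What to change.** In Appendix H Step 4, insert `proc sort data=Diff_imp; by parameter _imputation_; run;` before the second PROC MIANALYZE, and add `by parameter;` inside it. The output then has five rows, each pooled over 40 imputations. A check that the pooled-difference dataset has five rows per endpoint and 40 imputations per row would confirm it, and one run in SAS settles the question about the procedure's behaviour. Because the control-based method uses the same step, one correction serves both analyses. The cost is two statements of code; design, data collection and all other analyses stay as they are.
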